## BACKGROUND

Antimicrobial stewardship programs (ASPs) often restrict their activities to inpatient antimicrobial-prescribing. However, at least 40% of all antimicrobial exposure associated with an acute-care hospital stay is prescribed at the time of hospital discharge (i.e., post-discharge). Post-discharge antimicrobials mediate clinical outcomes after discharge and may facilitate the spread of antimicrobial resistance.

Several studies have shown that post-discharge antimicrobial use is often inappropriate. We used national data to show that 61% of fluoroquinolone treatment days were prescribed at hospital discharge; manual chart reviews at 9 hospitals found that 40% of these post-discharge fluoroquinolone prescriptions were either unnecessary or sub-optimal. Other studies have found that 53-79% of all post-discharge antimicrobials are either unnecessary or sub-optimal.

Post-discharge antimicrobials are an important target for antimicrobial stewardship. However, inpatient stewardship metrics do not capture post-discharge antimicrobials and ASPs frequently do not evaluate these prescriptions. A 2016 Veterans Health Administration (VHA) survey found that less than 50% of hospitals routinely reviewed targeted antimicrobials at discharge. According to a 2016 survey in Michigan, only 17% of 48 hospitals had a process for reviewing outpatient antimicrobial orders at discharge. Nearly all hospitals responding to these two surveys reported that they had an inpatient ASP.

We currently do not know how inpatient ASP resources can be effectively leveraged to improve post-discharge antimicrobial use. Several randomized-controlled trials have demonstrated that post-prescription audit-and-review (PPR) can reduce and improve inpatient antimicrobial use, but these studies did not measure the effect of PPR on post-discharge antimicrobial use. Two single-center non-randomized studies, including a study by our team of investigators, showed that inpatient PPR can decrease and improve post-discharge antimicrobial use. However, these findings may not be generalizable to other settings.

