### **Intervention activities:**

During the intervention, a study team member (either a physician or pharmacist) will perform discharge-PPR every weekday for patients on select medical services who are receiving an antimicrobial and whose discharge is anticipated within the next 48 hours. The number of services selected for PPR will be aimed at providing approximately 200 discharges per month per facility.

The site PI will provide physician-support for these PPR activities. Discharge-PPR audits will focus on optimizing antimicrobial selection, dose, and duration before discharge. The pharmacist will communicate all recommendations resulting from the audit to the primary prescribers. Site PIs and pharmacists will also participate in the collaborative learning calls every month during their sites' intervention periods.

All hospitals may continue their usual stewardship activities during the trial. However, hospitals will be strongly encouraged to not start any other new stewardship interventions targeting antimicrobial-prescribing at discharge.

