### **Objectives:**

AIM 1: Evaluate whether discharge post-prescription audit-and-review (PPR) can safely reduce post-discharge antimicrobial use across participating hospitals.

Hypothesis 1: The discharge audit-and-feedback intervention will reduce post-discharge antimicrobial use without adversely affecting patient safety.

AIM 2: Through monthly collaborative learning calls with participating sites, determine barriers and facilitators encountered by antimicrobial stewardship teams in their implementation of the discharge-PPR process.

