#### **Secondary outcomes**

Additional outcomes will include inpatient antimicrobial use (inpatient LOT per 100 admissions), length of stay, and 30-day hospital re-admission rates. These secondary outcomes will only be measured for patients who were discharged from a participating service or ward.

*Process measures:* Each day, the study pharmacist will record the number of patients audited during discharge-PPR, the number of PPR recommendations communicated to providers, and the number of recommendations that were accepted.

*Implementation outcomes:* We will use the RE-AIM framework to assess our intervention. Feasibility will be evaluated on 2 domains: 1) the development of a local process to identify patients who are on antimicrobials within 48 hours of hospital discharge, and 2) the initiation of the discharge-PPR intervention. To further understand the implementation process, the study coordinator will take notes during the collaborative learning calls. We will also record these calls. We will perform a rapid template analysis to describe each site's implementation process, including barriers and facilitators to successful implementation. Through a weekly survey, we will also assess each site's fidelity to the discharge-PPR process and the cost (i.e. time) of the intervention. Through a post-intervention electronic survey, we will assess the acceptability of discharge-PPR to frontline prescribers.

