### **Sample Size:**

We will calculate the average post-discharge LOT per 100 admissions every two weeks and will include 10 sites. For these power calculations, we assume: 1) an intra-cluster correlation of 0.75; 2) an effect size of 10% from the baseline average post-discharge LOT per 100 admission of 135; 3) 100 discharges per site every two weeks; ; 4) a cluster-level standard deviation of 3.4; 5) a Type I error rate of 5%, and 6) a constant treatment effect regardless of exposure time. Given these assumptions, under a stepped wedge study design with 1) each step lasting 2 weeks (24 measurements/site over 48 weeks total); 2) all 10 facilities starting in control status and 1 facility crossing into intervention status every 2 weeks following a baseline period of 24 weeks and ending with all facilities in intervention status in the final two-week block, we have more than 90% power to determine a statistical difference when discharge-PPR is used.

**Blinding:** None

**Unit of Analysis:** Each medical center

**Statistical Methods:** We will evaluate the effectiveness of implementing a discharge-focused process for post-prescription audit-and-review (PPR) via a generalized linear mixed model with identity link. The primary outcome will be post-discharge length of therapy (LOT) per 100 admissions. This model will include step and intervention indicators as fixed effects and a random intercept for cluster to account for facility-level factors. This model structure can provide proper weighting when cluster sizes vary and account for repeated measurements over time. Confounding variables (select covariates that may be associated with optimal antimicrobial prescribing) will be adjusted for statistically by inclusion in the model framework.

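### 30-day re-admission, the only listed outcome that can show harm after discharge, is counted in all discharges, which dilutes harm in the audited patients; an added analysis in inpatient antimicrobial recipients would recover part of the loss

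*Combined protocol and SAP*

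**What the plan says.** Under Objectives, Hypothesis 1 has two halves: "The discharge audit-and-feedback intervention will reduce post-discharge antimicrobial use without adversely affecting patient safety". The Background gives the reason safety matters here: "Post-discharge antimicrobials mediate clinical outcomes after discharge".

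The primary outcome is post-discharge length of therapy (LOT) per 100 admissions. Under Secondary outcomes: "Additional outcomes will include inpatient antimicrobial use (inpatient LOT per 100 admissions), length of stay, and 30-day hospital re-admission rates". The population for these is then fixed: "These secondary outcomes will only be measured for patients who were discharged from a participating service or ward". Nothing restricts it to patients who received an antimicrobial.

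The intervention is narrower. Under Intervention activities, audits are done on weekdays for "patients on select medical services who are receiving an antimicrobial and whose discharge is anticipated within the next 48 hours". They cover drug selection and dose as well as duration.

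The Sample Size section powers the trial on LOT, assuming "an effect size of 10% from the baseline average post-discharge LOT per 100 admission of 135". Statistical Methods describes a mixed model with step and intervention as fixed effects and a random site intercept. It names LOT as the primary outcome and does not mention re-admission. No section ties re-admission to the safety half of Hypothesis 1 or gives it an expected rate or a precision.

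**The concern.** Inpatient LOT and length of stay are complete when the patient leaves, so neither can show harm from a post-discharge course that was cut or changed. That leaves re-admission. Its denominator includes every discharge from the participating services, and patients who were not on an antimicrobial cannot be affected by the audit. Their re-admissions add noise and pull the estimated difference towards zero.

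The conclusion about safety is at stake. If harm occurs in a small share of discharges, the all-discharge difference can be small and non-significant, and a reader could take that as support for the second half of Hypothesis 1.

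**Working it through.** **Inputs from the documents.** 10 sites; 24 two-week blocks; 12 baseline blocks, then one site crossing per block (blocks 13–22); 100 discharges per site per block; effect 10% of 135 = 13.5 days per 100 admissions; type I error 5% (taken as two-sided). This gives 10 × 24 × 100 = 24,000 discharges. Of the 240 site-blocks, 75 are under intervention (12 + 11 + … + 3), or 7,500 discharges.

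**Assumed, because the documents do not say.** Re-admission rate p (15%, range 5–20%); mean cut d among shortened courses (1, 2 or 4 days); a 10-point rise in re-admission in the affected patients; the share g of discharges with an inpatient antimicrobial day (25–50%).

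**The plan's own figure.** With fixed block effects and a random site intercept, reading the stated SD of 3.4 on the per-100 scale as total, between-site or residual, the SE for LOT is 0.47, 0.54 or 0.94 days per 100. Against 13.5, power is about 100%, consistent with the stated figure of more than 90%. The unit of 3.4 is not given; that is a separate matter.

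**Re-admission, all discharges.** In the same design with binomial variance and no site-by-period variation:

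SE = 0.2767 × √(p(1−p)/100)

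At p = 0.15: 0.2767 × √(0.1275/100) = 0.99 points; half-width 1.96 × 0.988 = 1.94 points.

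If no course is lengthened, shortened patients per 100 = 13.5/d. Overall rise δ = (13.5/d) × 0.10 points. Power = Φ(δ/SE − 1.96) + Φ(−δ/SE − 1.96).

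| Mean cut | Shortened per 100 | δ (points) | Power |
|---|---|---|---|
| 1 day | 13.5 | 1.35 | 27.7% |
| 2 days | 6.75 | 0.68 | 10.5% |
| 4 days | 3.4 | 0.34 | 6.3% |

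**Sensitivity.** Baselines of 5–20% were combined with no site-by-period variation, or with ICC 0.01 or 0.05 and cluster autocorrelation 0.8. The probability of a non-significant result is 80–94% for 2- to 4-day cuts and 39–86% for a 1-day cut. With 10 sites these normal-based figures are optimistic.

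**A wider affected share.** If the mean post-discharge course is 5 days (assumed), 135/5 = 27 per 100 discharges leave on an antimicrobial. A 10-point rise in all of them gives δ = 2.7; 2.7/0.988 = 2.73; power 78.0%.

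**Restricted population, share g.** If all shortened patients fall inside it and the baseline rate is the same, the signal becomes δ/g and the SE becomes SE/√g. Signal relative to SE therefore rises by 1/√g: 1.4 times at g = 0.5 and 2.0 times at g = 0.25.

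| | All discharges | g = 0.5 | g = 0.25 |
|---|---|---|---|
| SE (points) | 0.99 | 1.40 | 1.98 |
| Half-width (points) | 1.94 | 2.74 | 3.87 |
| Power, 1-day cut | 27.7% | 48.9% | 78.0% |
| Power, 2-day cut | 10.5% | 16.2% | 27.7% |
| Power, 4-day cut | 6.3% | 7.7% | 10.5% |

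**The case against.** **The affected share may be larger than LOT implies.** Audits also change drug and dose, which can expose a patient to harm without altering duration, and the 10% effect is a planning assumption. So 13.5 per 100 does not cap the patients at risk. This stands, and it is why the 27% case is shown.

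**The size rests on assumptions.** Rate, share, mean cut and harm are all assumed. This stands too. A reader might infer that the all-discharge difference will be near zero whether or not patients are harmed, or that the trial cannot test safety at all. The documents do not support either reading: power is 61% for a 1-day cut at a 5% baseline, and 78% for a 10-point rise in 27% of discharges at a 15% baseline.

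**All discharges is a defensible population.** It matches the wards and the per-admission denominator of the primary outcome, and it avoids selection. A reader might call the choice an error. It is not one, and it should stay; the point is to add a second population.

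**It is a pilot, and outcomes are covered elsewhere.** The RE-AIM table's Effectiveness row refers to the primary and secondary outcomes, and re-admission is the only candidate for safety, so naming it is a one-line clarification. No section says that a non-significant result will be read as safety, and that intention should not be attributed to the sponsor. Hypothesis 1 still makes the claim.

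**The remedy is modest.** For a 4-day cut the gain is slight, and patients with any inpatient antimicrobial day are a broader group than the audit's target. Both stand, which is why the added analysis is only a partial answer.

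**Conclusion.** The concern holds in a conditional form. Three parts need no assumption: Hypothesis 1 claims safety; re-admission is the only listed outcome able to show post-discharge harm; and it is counted in all discharges although audits act only on antimicrobial recipients. Dilution follows from these.

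Its size depends on values that the documents do not give. At a 15% re-admission rate the trial resolves about ±1.9 points overall. A 10-point rise limited to shortened courses would usually be missed (power about 28% or less), while the same rise in about a quarter of discharges would usually be found. An additional analysis in antimicrobial recipients improves signal relative to SE by 1.4–2.0 times if 25–50% of discharges qualify. It is worth making but does not by itself secure a safety conclusion.

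**What to change.** 1. Name 30-day re-admission as the outcome for the safety half of Hypothesis 1.
2. Keep the all-discharge analysis. Add a pre-specified analysis in patients with at least one inpatient antimicrobial day in that stay or, if the data allow, in patients on an antimicrobial near discharge. Identify them the same way in control and intervention blocks. Do not define the group by a discharge prescription, because the intervention changes who receives one.
3. Use the same stepped-wedge model for both populations and report each difference with its 95% CI.
4. State in advance that non-significance is not read as safety, and limit the safety conclusion to the increases that the interval excludes.

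**Cost.** Sites must link re-admission to antimicrobial receipt at patient level when they extract data. Inpatient LOT is already planned, but as a rate per 100 admissions, and the documents do not show that this link exists. The restricted interval is wider (half-width 2.7–3.9 points against 1.9, under the assumptions above). The safety conclusion may turn out weaker than Aim 1 now implies.

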### **Sample Size:**

We will calculate the average post-discharge LOT per 100 admissions every two weeks and will include 10 sites. For these power calculations, we assume: 1) an intra-cluster correlation of 0.75; 2) an effect size of 10% from the baseline average post-discharge LOT per 100 admission of 135; 3) 100 discharges per site every two weeks; ; 4) a cluster-level standard deviation of 3.4; 5) a Type I error rate of 5%, and 6) a constant treatment effect regardless of exposure time. Given these assumptions, under a stepped wedge study design with 1) each step lasting 2 weeks (24 measurements/site over 48 weeks total); 2) all 10 facilities starting in control status and 1 facility crossing into intervention status every 2 weeks following a baseline period of 24 weeks and ending with all facilities in intervention status in the final two-week block, we have more than 90% power to determine a statistical difference when discharge-PPR is used.

**Blinding:** None

**Unit of Analysis:** Each medical center

**Statistical Methods:** We will evaluate the effectiveness of implementing a discharge-focused process for post-prescription audit-and-review (PPR) via a generalized linear mixed model with identity link. The primary outcome will be post-discharge length of therapy (LOT) per 100 admissions. This model will include step and intervention indicators as fixed effects and a random intercept for cluster to account for facility-level factors. This model structure can provide proper weighting when cluster sizes vary and account for repeated measurements over time. Confounding variables (select covariates that may be associated with optimal antimicrobial prescribing) will be adjusted for statistically by inclusion in the model framework.

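### On the usual per-100 readings, an SD of 3.4 with an ICC of 0.75 implies less noise than 100 discharges allow, so the power statement cannot be verified from its inputs

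*Combined protocol and SAP*

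**What the plan says.** The Sample Size section sets the scale of the calculation: "We will calculate the average post-discharge LOT per 100 admissions every two weeks". It then assumes "an intra-cluster correlation of 0.75; 2) an effect size of 10% from the baseline average post-discharge LOT per 100 admission of 135", "100 discharges per site every two weeks", "a cluster-level standard deviation of 3.4", a 5% type I error rate and a treatment effect that does not change with exposure time. The design has ten sites and 24 two-week blocks, with one site crossing per block "following a baseline period of 24 weeks". The conclusion is that "we have more than 90% power to determine a statistical difference when discharge-PPR is used".

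The block size agrees with the Intervention activities section, where service selection is "aimed at providing approximately 200 discharges per month per facility". LOT per 100 admissions is the only outcome scale named, both here and under Primary outcome. The Statistical Methods paragraph specifies fixed step and intervention effects with a random intercept for site.

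The SD is labelled as cluster-level. The plan does not say whether it is a total, between-site or residual SD, what its units are, or where it comes from. It does not say whether the ICC applies to patients or to site-block values, or whether the test is one- or two-sided.

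**The concern.** A two-week rate built from 100 discharges carries sampling noise that cannot fall below a minimum set by its mean. An SD of 3.4 on a mean of 135 looks too small to contain that noise, and more so if three quarters of the variance is assigned to stable differences between sites.

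The power statement is the plan's only stated basis for the trial's size. If its variance inputs cannot all hold, it says nothing reliable about the chance of detecting a 10% reduction. A null result could still be read from its confidence interval, but this power statement could not be cited in support of it.

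**Working it through.** **Inputs.** From Sample Size: 10 sites; 24 blocks; crossing at blocks 13 to 22; target 10% of 135 = 13.5 per 100; 100 discharges per site-block; ICC 0.75; SD 3.4; 5% error, taken as two-sided with normal critical values. Assumed, because the plan does not say: LOT counted in whole days, independent patients, one admission per discharge.

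**1. Standard error under the planned model.** For between-site SD τ and site-block residual SD σ,

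SE² = I σ²(σ² + Tτ²) / [(IU − W)σ² + (U² + ITU − TW − IV)τ²],

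with I = 10, T = 24, U = 75, W = 585, V = 645. Then IU − W = 165 and the second bracket is 3135. So SE/σ = √(240/3135) = 0.2767 when τ is large and √(10/165) = 0.2462 when τ = 0. Power = Φ(13.5/SE − 1.96).

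**2. The plan's own figure.** Take 3.4 per 100 and a site-block ICC of 0.75:

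| 3.4 read as | Residual SD | SE | 13.5/SE | Power |
|---|---|---|---|---|
| total SD | √(0.25 × 11.56) = 1.70 | 0.470 | 29 | about 100% |
| between-site SD | 3.4/√3 = 1.96 | 0.542 | 25 | about 100% |
| residual SD | 3.40 | 0.939 | 14 | about 100% |

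Power above 90% therefore follows from these inputs.

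**3. Minimum sampling noise.** A whole-day count with mean 1.35 has its smallest variance when every patient gets 1 or 2 days: 0.35 × 0.65 = 0.2275, an SD of 0.477 days. Per 100 admissions with 100 discharges this is 0.477 × 100/√100 = 4.77 (variance 22.75). At the target mean of 1.215 it is √(0.215 × 0.785) × 10 = 4.11. All three residual SDs in step 2 are below both values. The minimum falls to 3.4 only at 100 × 22.75/11.56 ≈ 197 discharges per block.

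**4. The ICC that 3.4 would allow.** With 3.4 as the between-site SD, the site-block ICC is at most 11.56/(11.56 + 22.75) = 0.34. An ICC of 0.75 at the minimum noise needs a between-site SD of about √3 × 4.77 = 8.3.

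**5. What 90% power requires.** Solving step 1 for 90% gives a residual SD of 15.1 (large τ), 16.0 (τ = 3.4) or 16.9 (τ = 0). With 100 discharges these are within-site patient SDs, zeros included, of about 1.5 to 1.7 days. At the minimum of 4.77 power is still about 100%. With Poisson-like variation (assumed; √1.35 = 1.16 days) it is about 99%.

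**6. Patient-day readings.** If 3.4 is in days and 0.75 is a patient-level ICC, the site-block residual SD is 17.0 (3.4 as total), 19.6 (between-site) or 34 (within-site). Two-sided power is 82%, 70% or 30%; one-sided it is 89%, 80% or 42%. With a site-block ICC, two-sided power is 30% to 31%.

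**The case against.** The strongest defence is that the claim reproduces. Step 2 gives about 100% power, and so does the minimum-noise value itself. It would be wrong to say that the stated inputs fail to yield more than 90%.

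Nor do 3.4 and 0.75 conflict with each other. Any SD can be paired with any ICC; the conflict appears only when the sampling minimum is added, and that rests on assumptions the plan does not state. These points stand. The assumptions are mild, however: the minimum supposes that every patient receives exactly 1 or 2 days, and positive correlation between patients would raise it.

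Non-standard per-100 readings can also be coherent:

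- Let 3.4 be the SD of true site-block rates and 0.75 their correlation between blocks, with sampling noise added separately. Power is then at least 90% up to a sampling SD of 16.0. That sampling SD is not in the plan, and the ICC of the analysed values would be at most 0.75 × 11.56/(11.56 + 22.75) = 0.25.
- Let 3.4 be the SD of site averages, with 0.75 the between-site share of that variance. Noise in a site average is then 1.7, block noise is 1.7√12 = 5.9 or 1.7√24 = 8.3, and power exceeds 99.9%. This is not the usual definition of an ICC, and the plan does not give it.

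A reader might infer from the 30% to 82% figures in step 6 that the trial is underpowered. The documents do not support that. The cluster-level label and the only named scale both disfavour patient days, and with a patient-level ICC these readings need a between-site SD of at least 2.9 days on a mean of 1.35.

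Finally, the documents describe a pilot with a fixed set of ten sites, so the practical consequence is limited. That bears on severity; it does not make the inputs consistent.

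**Conclusion.** The point holds in a limited form. On the standard readings in LOT per 100 admissions, the mean, block size, SD and ICC imply a residual SD of 1.7 to 3.4 against a minimum of about 4.8, so they cannot all be true. This depends on whole-day LOT, independent patients and one admission per discharge. The stated power is arithmetically reproducible but cannot be verified, because the quantity that decides it, the within-site SD including sampling noise, is missing.

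The documents do not establish a shortfall. Power is 90% or more if the within-site patient SD is at most about 1.5 to 1.7 days, depending on the between-site variance, and lower if it is larger. This should be fixed, but it does not undermine the design or the planned model.

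**What to change.** In Sample Size, replace assumptions 1 and 4 with:

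- a within-site SD with its units (days per patient, or site-block per 100) that includes the sampling variance from 100 discharges;
- a between-site SD, or an ICC with its level stated;
- the source of each.

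State in assumption 5 whether the test is one- or two-sided. Estimate the variance inputs from the 24-week all-control period (10 sites × 12 blocks × about 100 = about 12,000 discharges) before any intervention data are examined. Restate power, or the detectable difference, as a sensitivity table that names its between-site variance. For example, two-sided power for 13.5 per 100:

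| Within-site patient SD (days) | Large between-site variance | Between-site SD 3.4 per 100 | None |
|---|---|---|---|
| 1.16 | 99% | 99% | 99.7% |
| 1.51 | 90% | 93% | 95% |
| 1.70 | 82% | 86% | 90% |
| 2.22 | 59% | 66% | 70% |
| 2.76 | 42% | 49% | 51% |
| 3.40 | 30% | 35% | 36% |

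The cost is protocol wording and one recalculation. The stated power may become less favourable. No sites or patients are added, and the outcome and model stay as they are.
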